--	---

	
 - For Dercum's disease subjects – ultrasound assessing nodules size (diameter) and quality. - For lipedema subjects – measurement of leg circumference above the knee and assessing fat thickness and nodular quality by ultrasound. - Subjects will be questioned for AEs.

Safety Analysis
	
Safety data from the study will be summarized descriptively by treatment and cohort. Descriptive statistics will be calculated for quantitative data and frequency counts and percentages will be provided for categorical data. The nature, frequency, seriousness, severity and relation to study drug of AEs will be tabulated for all subjects combined and by treatment. Change-from-baseline values for vital signs, clinical laboratory and ECG will be summarized. Shift tables of normal / abnormal versus baseline may be presented as well. Draize scores will be presented in tabular format by visit, treatment, and cohort. Serious adverse events (SAEs) will be described in narratives as part of the study report.

Study Endpoints
	
Primary Endpoint: Evaluation of the overall safety of RZL-012 injection into the subcutaneous fat in Dercum's disease and lipedema. The primary safety endpoint is the incidence of intolerable side effects.
 
Secondary Endpoints:
 
 1. For lipedema subjects - The reduction in local subcutaneous fat in the injection site region as compared to baseline based on ultrasound (reduction in nodules size and/or numbers) and leg circumference above the knee assessments. 2. For Dercum's disease subjects - The reduction in local subcutaneous fat in the injection site region as compared to baseline based on ultrasound (reduction in nodules size and/or numbers). 3. Extended duration of the fat reduction effect. To that end, ultrasound images and above the knee circumference measurement will be followed for 56 days. 4. Elucidation of the tissue changes by ultrasound of the injection site to include reduction in fat thickness and nodular quality. 5. Improvement in local pain as measured by Comparative Pain Scale and by the reduction in the use of analgesics. 6. Improvement in QOL and function in lipedema subjects as measured by questionnaire (such as The Lower Extremity Functional Scale (LEFS)).

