Sample Size	This study is planned as a Phase 2a trial. A maximum of 12 evaluable subjects will be included in the study (6 Dercum's disease subjects and 6 lipedema subjects) and followed for as long as 56 days.
Statistical Methods	
Statistical analyses will be mainly descriptive in nature where study data will be tabulated and summarized using the mean, standard deviation or standard error, median, minimum, maximum and number of subjects by cohort for continuous data. For categorical data, results will be summarized via a count and percentage by cohort. The results will be presented overall, per cohort and per cohort and dose. The effects of noncompliance, dropouts, and covariates may be assessed to determine the impact on the general applicability of results from this study.
 
If any statistical tests are performed, they will be two-sided. The required significance level of findings will be equal to or lower than 5%. Nominal p-values will be presented.
 
Where confidence limits are appropriate, the confidence level will be 95%.
 
Incidence of intolerable side effects will be tabulated by study drug by cohort along with 95% confidence intervals.
 
Change from baseline will be presented in a tabular form by visit treatment.
 
AEs and tolerability data will be presented descriptively by treatment and cohort. AEs will be tabulated by body system, preferred term, seriousness, severity and relation to study drug by cohort. Where applicable, changes in values over time (e.g., lab values, vital signs, ECGs) will be presented; this will include clinical laboratory evaluations (including CBC, blood chemistry and urinalysis), coagulation (INR, PTT and PT), vital signs, and ECGs. Shift tables of normal / abnormal versus baseline may be presented as well.
 
Draize scores will be presented in tabular format by visit, treatment, and cohort

Study Duration	
Study duration is 2.5 months, including enrollment, treatment and follow-up period.
 
Each subject will participate in the study for up to 42 days as part of this protocol.

Study Site	University of Arizona Medical Center, Tucson, Arizona

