6.1.15. Adverse Events

The information obtained during weekly subjects questioning, review of subject's compliance record, physical examinations, vital signs measurements, blood testing, and by any other means will be evaluated in light of baseline medical data and thus provide the basis for adverse events identification and grading.

The trial will proceed within a cohort and from one cohort to the next as long as no more than one subject experiences intolerable side effects and based on the decision made by the PI. Proceeding from one subject to the next will be based on the decision made after reviewing all safety data collected by Day 7 within 2 ± 1 d of the last dosed subject in each cohort.

The AEs reported during the trial will be graded (see Section 9), documented, and assessed in light of their clinical significance and relation to investigational product. In addition, the following information regarding the AE must be obtained: AE description, start date, end date (if applicable) or ongoing, severity, seriousness, relationship to study drug, outcome (e.g., resolved / unresolved), and action taken (e.g., concomitant medication). The sponsor or the sponsor representative will provide information regarding serious adverse event (SAE) expectedness based on data included in the IB. AE monitoring will be conducted throughout subject's participation up to 56 days after injection.

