9.5. ADVERSE EVENT REPORTING AND MONITORING REQUIREMENTS

9.5.1. General

All AEs, serious and non-serious, will be fully documented in both source documents and CRFs as described in Section 6.1.13, and each AE will be assessed in light of its clinical significance. For each AE, the investigator will provide the onset, end, intensity, treatment required, outcome, seriousness and action taken with the investigational drug. The investigator will determine the relationship to the investigational drug, i.e., causality assessment, for each AE.

Any AE occurring prior to initiation of first dose, after initiation of the first dose and or during any point throughout the study should be recorded on the AE page of the CRF. All AEs occurring until subject is terminated from the study (28 days after the injection of RZL-012 and in the highest dose cohort until 6 months from injection of RZL-012), should be captured in the CRF. AEs should be recorded in the CRF using the medical terminology found in the source documentation. Whenever possible, diagnoses should be given when signs and symptoms are due to a common etiology.

Occurrence of any Grade 4 and Grade 3 or 4 ADR must warrant clinical evaluation by the treating investigator and reported to the Sponsor within 7 calendar days.

ADRs graded > 1 will be followed-up until resolution, or for a maximal duration of 6 months after RZL-012 injection, whichever occurs first.

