10.2. STUDY ENDPOINTS

10.2.1. Primary Safety Endpoints

The primary safety endpoint is the incidence of intolerable side effects and AEs.

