10.5.2. Subject Disposition

A detailed description of subject accountability including count of subjects included, exposed, completed (i.e., subjects who complete the study treatment) and discontinued along with the main reason for discontinuation will be generated for each cohort and for all subjects. All withdrawals from the study, taking place on or after study drug injection, will be fully documented in the body of the Clinical Study Report.

Note that the actual study duration is for a period of maximum 2 months, with efficacy analyses being conducted at 28 days and 56 days.

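### AE capture ends at Day 28, Day 56 or 6 months depending on the section, and no single analysis window is set for the primary safety incidences

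*Protocol*

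**What the plan says.** The current text gives several end points for AE observation.

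- Protocol 9.5.1 captures all AEs until the subject is terminated from the study, which it puts at "28 days after the injection of RZL-012 and in the highest dose cohort until 6 months from injection of RZL-012".
- Protocol 6.1.15 has AE monitoring "up to 56 days after injection", with no distinction by dose. Table 2 lists AE assessment at Day 56, and the synopsis says of the Day 56 visit: "Subjects will be questioned for AEs".
- The synopsis says subjects are "followed for as long as 56 days" under Sample Size, but under Study Duration: "Each subject will participate in the study for up to 42 days as part of this protocol".
- Protocol 10.5.2, repeated in SAP 5.8.9, says: "Note that the actual study duration is for a period of maximum 2 months".

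The start is also open. Section 9.5.1 puts on the AE page of the CRF "Any AE occurring prior to initiation of first dose, after initiation of the first dose and or during any point throughout the study".

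Protocol 10.2.1 states: "The primary safety endpoint is the incidence of intolerable side effects and AEs". Protocol 10.5.4 and SAP 5.8.13 report intolerable side effects as proportions with exact 95% intervals, overall and by cohort. The SAP 14.4.1 table shells give AE frequencies. Protocol 10.5.1 and SAP 5.8.2 have results shown overall, by cohort, and by cohort and dose. None of these sections gives a cut-off day or a treatment-emergent definition.

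**The concern.** A crude incidence has no clear meaning without a stated period. Here the period is open, and one reading of the protocol makes it depend on dose. If 9.5.1 governs, the higher-dose subjects are observed for 6 months and the rest for 28 days. With equal hazards, the expected any-AE incidence in the longer-observed group can then only be equal or higher. A reader of the by-dose AE tables could take a difference in observation time for a dose effect. If Day 56 governs, there is no such imbalance.

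The two parts of the endpoint are affected differently. An intolerable side effect must be judged possibly or probably related to the drug (protocol 3.3.2), so pre-dose and unrelated events cannot count towards it. The window still decides whether a late related event enters the numerator. Pre-dose events can inflate only the any-AE counts, and they do so in all groups alike.

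**Working it through.** **1. End points side by side**

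| Source | End of observation | Who |
|---|---|---|
| Protocol 9.5.1 | 28 days | all but the highest-dose cohort |
| Protocol 9.5.1 | 6 months | highest-dose cohort |
| Protocol 6.1.15, Table 2, synopsis visits | Day 56 | everyone |
| Protocol 10.5.2, SAP 5.8.9 | at most 2 months | everyone |
| Synopsis, Study Duration | 42 days of participation | everyone |

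Screening may start on Day -14. A Day 56 visit therefore needs up to 14 + 56 = 70 days of participation. The stated 42 equals 14 + 28, which would match the Day 28 rule, although no section derives it that way. No visit is scheduled after Day 56.

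Three other periods do not settle the matter. The 14-day period in 3.2 governs escalation. Days 28 and 56 in SAP 5.8.9 are efficacy time points. The 6-month follow-up of ADRs above grade 1, also in 9.5.1, concerns events already recorded.

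**2. Who is in the highest-dose cohort**

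Cohort 1 is Dercum's disease, up to 40 mg. Cohort 2 is lipedema, with 60 mg and 80 mg (three subjects each in 3.2). The phrase could mean the three subjects at 80 mg or all six in cohort 2. Either way, the longer window falls on higher doses.

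**3. Observation time if 9.5.1 governs** (6 months taken as 182 days)

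- Window ratio: 182/28 = 6.5.
- 80 mg only: 3 × 182 = 546 person-days against 9 × 28 = 252, so a quarter of the subjects supply 546/798 = 68%.
- All of cohort 2: 6 × 182 = 1092 against 6 × 28 = 168, or 1092/1260 = 87%.
- With Day 56 for everyone: 12 × 56 = 672, of which 80 mg supplies 168/672 = 25%.

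**4. Effect on the any-AE incidence with no drug effect**

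The documents give no AE rate, so the 28-day risk p is an assumption. Let f be the share of the 182-day cumulative hazard that falls in the first 28 days. Then

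risk at 182 days = 1 − (1 − p)^(1/f).

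| p | f = 1 | f = 0.75 | f = 0.5 | constant hazard, f = 28/182 |
|---|---|---|---|---|
| 10% | 10% | 13% | 19% | 50% |
| 20% | 20% | 26% | 36% | 77% |
| 30% | 30% | 38% | 51% | 90% |
| 80% | 80% | 88% | 96% | – |
| 90% | 90% | 95% | 99% | – |

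Example: p = 10% and constant hazard gives 1 − 0.9^6.5 = 0.50. Protocol 1.2.4 reports that most phase 0 AEs linked to injection were local and transient, so the columns with more early hazard are more plausible.

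**5. Effect on intolerable side effects**

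Suppose one related event has its onset after Day 28 (exact Clopper-Pearson 95% intervals).

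- Cohort of six: 0/6 = 0% (0 to 45.9%) becomes 1/6 = 16.7% (0.4 to 64.1%).
- Dose level of three: 0/3 = 0% (0 to 70.8%) becomes 1/3 = 33.3% (0.8 to 90.6%). The plan specifies the exact interval overall and by cohort only; the dose-level intervals are shown for scale.

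There is a concrete route to an ambiguous case. In 3.3.2, grade 3 and 4 ALT/AST elevations must last beyond 10 days, and the last scheduled chemistry is on Day 28. An elevation first found on Day 28 could qualify only after Day 38. Whether it counts depends on the window and on whether onset or grading date is used, and the plan states neither.

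**The case against.** The strongest reply is that Day 56 is already implied. Section 9.5.1 also asks for AEs at any point in the study. The Day 56 visit with AE questioning appears in several places, and the SAP schedule has a Day 56 column. The synopsis gives a study duration of 2.5 months, which read per subject fits the 70 days above. On this view the parenthesis in 9.5.1 is a leftover and the dose imbalance is hypothetical. Capture after Day 56 would rest on unscheduled reports, so 6.5 times the calendar time is not 6.5 times the ascertainment. Local reactions are expected early and often; from a risk of 80% or 90% the shift is too small to see in three subjects. The analyses are mainly descriptive, no between-dose test is planned, and onset dates allow the window to be applied later.

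Much of this stands as a limit on size. Day 56 is the likelier intention, the constant-hazard figures are an upper case, and a high early AE rate leaves little room for inflation. It does not remove the problem. The 28-day and 6-month rule is current text, it covers all AEs, and a site that follows it stops capture at Day 28 for most subjects. Events not captured cannot be placed in a window afterwards. SAP 5.8.6 lets the SAP govern how data are handled, but the SAP sets no window. In a safety trial of 12, a descriptive incidence still needs a stated period.

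**Conclusion.** The concern holds and should be fixed. The contradiction between 9.5.1 and the Day 56 sections is certain, as is the absence of an analysis window in both documents. The dose imbalance is conditional: it arises only if 9.5.1 is followed.

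In that case the window ratio is about 6.5. An assumed 10% any-AE risk at 28 days would read 10% to 19% at 6 months if at least half the hazard falls in the first 28 days, and up to 50% if the hazard is constant. These figures rest on the assumed risk, on equal hazards across doses and on equal ascertainment; weaker ascertainment after Day 56 or a high early AE rate would shrink the shift. For intolerable side effects the stake is whether a late related event counts, worth 16.7 percentage points in a cohort of six and 33.3 in a dose level of three.

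**What to change.** Reconcile protocol 9.5.1, 6.1.15, Table 2, 10.5.2 and the synopsis duration statements, and define or remove the highest-dose cohort. When doing so, also reconcile the dose-level sizes: 6.2.3.1 has three levels of two subjects and the cohort 2 table in 3.3.1 shows two and two, whereas the dosing text in 3.2 and 3.3.1 has three and three.

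Add to the SAP, in substance:

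- The primary incidence of intolerable side effects and AEs counts events with onset from injection on Day 0 through the Day 56 visit, identically for every subject and dose.
- Events with onset before injection are listed separately.
- Events with onset after Day 56 are reported separately. Any that are drug-related or intolerable are shown next to the primary table, by dose and onset day.

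Day 56 is proposed because it is the last scheduled AE assessment common to all subjects. Another common window could serve if it is stated in advance and capture supports it. This is an analysis window only and need not shorten any longer safety follow-up.

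The cost is wording in two documents: the Day 56 visit with AE questioning exists and onset dates are already collected. The downside is that a late event at the top dose leaves the primary incidence and appears in the adjacent display instead.

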9.5.2. SAE Reporting

The PI or his designee must report to the Sponsor any SAE occurring after injection of the study treatment, regardless of their relationship to the investigational product.

Sponsor contact details for SAE reporting:

[name], [contact], [contact].

An initial report must be faxed or emailed to [contact], [contact] within 24 hours of becoming aware of the event and must include SAE general description, start date, end date (if applicable), the reason for evaluation as a SAE, basic subject information, assessment of the relationship to the investigational product, expectedness, and study therapy information.

Follow-up information, including outcome and treatment, shall be faxed or emailed within 48 hours. Source documents to support the SAE (e.g., discharge summary, test results) shall be included in the report.

A complete SAE report must be sent to the Sponsor at the first possible date and no later than 7 calendar days after SAE end date. In addition to the information described in the initial report, this report will include CTCAE description and grading, treatment given (if applicable), SAE outcome, an assessment of the relationship to the investigational product, and expectedness.

SAE will be recorded on designated CRF forms in a timely manner and no later than 7 calendar days after its end date.

The PI or his designee will submit the SAE report to IRB/EC according to applicable local regulations and will update the Sponsor.

9.5.3. Expedited Reporting

Expedited reporting by PI to IRB/EC is warranted for all Suspected Unexpected Serious Adverse Reactions (SUSAR), i.e., unexpected SAEs that are considered related to study product as defined in Sections 9.1.2, 9.1.3, and 9.4). Additional cases will be communicated by PI to IRB/EC via expedited reporting when required by local regulation.

Expedited reports will be submitted to the applicable regulatory authorities by the Sponsor or designee within the required timelines according to local regulations.

Any pregnancy of a subject and of a partner of a study male subject after dosing is considered an immediate reportable event.

Such events must be reported within one (1) working day of the investigator becoming aware of the event. Pregnancies shall be followed for the duration of the pregnancy. It is the PI's

responsibility to provide to the Sponsor follow-up information on the outcome of the pregnancy including information about any sequelae.

10. STATISTICAL CONSIDERATIONS

10.1. STUDY DESIGN AND OBJECTIVE

This is an open label, 2 cohort, clinical trial in women with lipedema with substantial fat above the knee or women and men with nodular Dercum's disease. Each cohort will have 6 subjects who will receive RZL-012.

- The 1st cohort will be comprised of subjects with Dercum's disease
- The 2nd cohort will be comprised of subjects with lipedema with substantial fat above the knee.

Primary objective: Evaluation of the overall safety of RZL-012 following injection into the subcutaneous fat in patients with lipedema.

Secondary objective: Evaluation of local fat reduction, its extent, duration and tissue associated changes, in response to RZL-012 treatment, utilizing minimal invasive means (ultrasound) following subcutaneous injection of RZL-012 into fatty tissue below the skin.

10.2. STUDY ENDPOINTS

10.2.1. Primary Safety Endpoints

The primary safety endpoint is the incidence of intolerable side effects and AEs.

10.2.2. Secondary Efficacy Endpoints

Secondary efficacy endpoints include:

- For lipedema subjects - The reduction in local subcutaneous fat in the injection site region as compared to baseline based on ultrasound (reduction in nodules size and/or numbers) and leg circumference above the knee assessments.
- For Dercum's disease subjects - The reduction in local subcutaneous fat in the injection site region as compared to baseline based on ultrasound (reduction in nodules size and/or numbers).
- Extended duration of the fat reduction effect. To that end, ultrasound images and above the knee circumference measurement will be followed for 56 days.
- Elucidation of the tissue changes by ultrasound of the injection site to include reduction in fat thickness and nodular quality.

- Improvement in local pain as measured by Comparative Pain Scale and by the reduction in the use of analgesics.
- Improvement in QOL and function in lipedema subjects as measured by questionnaire (such as LEFS).

10.2.3. Safety and Tolerability Endpoints

Safety endpoints include:

- Incidence of AEs and SAEs, by severity and relation to study treatment. AEs will be coded using MedDRA version 19.1 (or higher).
- Physical examination (including Draize score)
- Vital signs
- Blood laboratory tests
- ECG

10.3. SAMPLE SIZE JUSTIFICATION

This study is planned following a 6 subjects per group paradigm. A maximum of 12 evaluable subjects will be included in the study (6 subjects with Dercum's disease and 6 subjects with lipedema) and followed for as long as 2 months.

10.4. ANALYSIS SETS

10.4.1. Safety Analysis Set (SA)

The SA will consist of all enrolled subjects who received the study treatment, (exposed population), including subjects prematurely withdrawn.

All enrolled subjects receiving at least one study drug injection are considered evaluable for the SA set.

10.4.2. Efficacy Analysis Set (EF)

The EF will consist of all subjects from the SA analysis set without any major protocol violations measured at baseline. Subjects will be analyzed according to the treatment received.

10.4.3. Statistical Analysis of Analysis Sets

The SA analysis set will serve as the principal data analysis set for the analyses of the safety endpoints.

The EF analysis set will serve as the principal data analysis set for the analyses of the efficacy endpoints.

10.5. STATISTICAL ANALYSIS

10.5.1. General

Statistical analysis will be performed using SAS V9.3 or higher (SAS Institute, Cary NC, USA).

Statistical analyses will be mainly descriptive in nature where study data will be tabulated and summarized using the mean, standard deviation or standard error, median, minimum, maximum and number of subjects by cohort for continuous data. For categorical data, results will be summarized via a count and percentage by cohort. The results will be presented overall, per cohort and per cohort and dose. The effects of noncompliance, dropouts, and covariates, may be assessed to determine the impact on the general applicability of results from this study.

If any statistical tests are performed, they will be two-sided. The required significance level of findings will be equal to or lower than 5%. Nominal p-values will be presented.

Where confidence limits are appropriate, the confidence level will be 95%.

